Appendix 2. Clinical Laboratory Tests

Safety Laboratory Tests

Hematology^a	Clinical Chemistry^a
Hematocrit	Sodium
Hemoglobin	Potassium
Erythrocyte count (RBC)	Calcium
Mean cell volume	Phosphorus
Mean cell hemoglobin	Glucose (random)
Mean cell hemoglobin concentration	Blood urea nitrogen (BUN)
Leukocytes (WBC)	Uric acid
Cell morphology	Total cholesterol
Absolute counts of:	Total protein
Neutrophils	Albumin
Lymphocytes	Total bilirubin ^c
Monocytes	Alkaline phosphatase (ALP)
Eosinophils	Aspartate aminotransferase (AST)
Basophils	Alanine aminotransferase (ALT)
Platelets	Creatinine
Urinalysis^a	
Specific gravity	Ethanol testing ^d
pH	Urine drug screen ^d
Protein	QuantiFERON-TB Gold test or TB T-Spot test ^{a,c}
Glucose	
Ketones	Serology^{e,f}
Bilirubin	Hepatitis B surface antigen
Urobilinogen	Hepatitis B core antibody
Blood	Hepatitis C antibody
Nitrite	HIV antibodies
Microscopic examination of sediment ^b	Serum Pregnancy test ^{g,h}
	Hormone Panel
	Follicle-stimulating hormone ^{e,i}

Abbreviations: HIV = human immunodeficiency virus; RBC = red blood cells; TB = tuberculosis; WBC = white blood cells.

- ^a Performed by local laboratory. Results will be validated by the local laboratory at the time of initial testing.
- ^b If clinically indicated, per investigator's discretion.
- ^c If total bilirubin is elevated, conjugated (direct) bilirubin and unconjugated (indirect) bilirubin may be measured.
- ^d Urine drug screen and ethanol level will be performed locally at screening and on Day -1 during admission to the clinical research unit. May be repeated at the discretion of the investigator.
- ^e Performed at screening only.
- ^f Performed by local laboratory at screening.
- ^g Serum pregnancy tests for all female subjects; women with confirmed postmenopausal status at Screening can be exempted from further pregnancy tests during the study.
- ^h Refer to Section 2 for specific sampling timing.
- ⁱ To be done for women to confirm postmenopausal status.

Appendix 3. Study Governance, Regulatory and Ethical Considerations

Informed Consent

The investigator is responsible for:

- ensuring that the subject understands the nature of the study, the potential risks and benefits of participating in the study, and that their participation is voluntary.
- ensuring that informed consent is given by each subject. This includes obtaining the appropriate signatures and dates on the informed consent form (ICF) prior to the performance of any protocol procedures and prior to the administration of investigational product.
- answering any questions the subject may have throughout the study and sharing in a timely manner any new information that may be relevant to the subject's willingness to continue his or her participation in the study.
- providing a copy of the ICF to the participant and retaining a copy on file.

Recruitment

Lilly, or its designee, is responsible for the central recruitment strategy for subjects. Individual investigators may have additional local requirements or processes. Study-specific recruitment material should be approved by Lilly.

Ethical Review

The investigator must give assurance that the ethical review board (ERB) was properly constituted and convened as required by International Council for Harmonisation (ICH) guidelines and other applicable laws and regulations.

Documentation of ERB approval of the protocol and the ICF must be provided to Lilly before the study may begin at the investigative site. Lilly or its representatives must approve the ICF before it is used at the investigative site. All ICFs must be compliant with the ICH guideline on good clinical practice (GCP).

The study site's ERB should be provided with the following:

- the current Investigator's Brochure and updates during the course of the study
- ICF
- relevant curricula vitae

Regulatory Considerations

This study will be conducted in accordance with the protocol and with:

- 1) consensus ethics principles derived from international ethics guidelines, including the Declaration of Helsinki and Council for International Organizations of Medical Sciences International Ethical Guidelines
- 2) applicable ICH GCP Guidelines

- 3) applicable laws and regulations

Some of the obligations of the Sponsor will be assigned to a third-party organization.

Protocol Signatures

The Sponsor's responsible medical officer will approve the protocol, confirming that, to the best of his or her knowledge, the protocol accurately describes the planned design and conduct of the study.

After reading the protocol, each principal investigator will sign the protocol signature page and send a copy of the signed page to a Lilly representative.

Final Report Signature

The final report coordinating investigator or designee will sign the clinical study report for this study, indicating agreement that, to the best of his or her knowledge, the report accurately describes the conduct and results of the study.

If the study is conducted at more than 1 site, the investigator with the most enrolled subjects will serve as the final report coordinating investigator. If this investigator is unable to fulfill this function, another investigator will be chosen by Lilly to serve as the final report coordinating investigator.

The Sponsor's responsible medical officer and statistician will sign/approve the final clinical study report for this study, confirming that, to the best of his or her knowledge, the report accurately describes the conduct and results of the study.

Data Quality Assurance

To ensure accurate, complete, and reliable data, Lilly or its representatives will do the following:

- provide instructional material to the study sites, as appropriate.
- provide training to instruct the investigators and study coordinators. This training will give instruction on the protocol, the completion of the electronic case report forms (eCRFs), and study procedures.
- make periodic visits to the study site.
- be available for consultation and stay in contact with the study site personnel by mail, telephone, and/or fax.
- review and evaluate eCRF data and/or use standard computer edits to detect errors in data collection.
- conduct a quality review of the database.

In addition, Lilly or its representatives will periodically check a sample of the subject data recorded against source documents at the study site. The study may be audited by Lilly and/or regulatory agencies at any time.

Investigators will be given notice before an audit occurs.

The investigator will keep records of all original source data. This might include laboratory tests, medical records, and clinical notes. If requested, the investigator will provide the Sponsor, applicable regulatory agencies, and applicable ERB with direct access to the original source documents.

Data Collection Tools/Source Data

An electronic data capture system will be used in this study. The site must define and retain all source records and must maintain a record of any data where source data are directly entered into the data capture system.

Data Protection

Data systems used for the study will have controls and requirements in accordance with local data protection law.

The purpose and use of subject personal information collected will be provided in a written document to the subject by the Sponsor.

Study and Site Closure

Discontinuation of Study Sites

Study site participation may be discontinued if Lilly or its designee, the investigator, or the ERB of the study site judges it necessary for medical, safety, regulatory, or other reasons consistent with applicable laws, regulations, and GCP.

Discontinuation of the Study

The study will be discontinued if Lilly or its designee judges it necessary for medical, safety, regulatory, or other reasons consistent with applicable laws, regulations, and GCP.

Appendix 4. Hepatic Monitoring Tests for Treatment-Emergent Abnormality

Selected tests may be obtained in the event of a treatment-emergent hepatic abnormality and may be required in follow-up with subjects in consultation with Lilly or its designee clinical research physician.

Hepatic Monitoring Tests

Hepatic Hematology^a

Hemoglobin

Hematocrit

RBC

WBC

Neutrophils

Lymphocytes

Monocytes

Eosinophils

Basophils

Platelets

Haptoglobin^a

Hepatic Coagulation^a

Prothrombin Time

Prothrombin Time, INR

Hepatic Serologies^{a,b}

Hepatitis A antibody, total

Hepatitis A antibody, IgM

Hepatitis B surface antigen

Hepatitis B surface antibody

Hepatitis B Core antibody

Hepatitis C antibody

Hepatitis E antibody, IgG

Hepatitis E antibody, IgM

Anti-nuclear antibody^a

Alkaline phosphatase isoenzymes^a

Anti-smooth muscle antibody (or anti-actin antibody)^a

Abbreviations: ALT = alanine aminotransferase; AST = aspartate aminotransferase; CPK = creatinine phosphokinase; GGT = gamma-glutamyl transferase; Ig = immunoglobulin; INR = international normalized ratio; RBC = red blood cells; WBC = white blood cells.

^a Assayed by Lilly-designated or local laboratory.

^b Reflex/confirmation dependent on regulatory requirements and/or testing availability.

Appendix 5. Blood Sampling Summary

The following table summarizes the approximate number of venipunctures and blood volumes for all blood sampling (screening, safety laboratories, and bioanalytical assays) during the study. Fewer venipunctures and blood draws may actually occur, but this will not require a protocol amendment.

Protocol I6T-MC-AMBD Sampling Summary

Purpose	Maximum Blood Volume per Sample (mL)	Maximum Number of Blood Samples	Maximum Total Volume (mL)
Screening tests ^a	19.5	1	19.5
Clinical laboratory tests ^a	12.5	6	75
Pharmacokinetics ^b	2	16	32
Immunogenicity ^a	10	4	40
Pregnancy tests	3.5	4	14
Total			180.5
Total for clinical purposes [rounded up to nearest 10 mL]			190

^a Additional samples may be drawn if needed for safety purposes.

^b Includes a potential 3 additional samples to be matched to additional immunogenicity samples (see Section 9.6.1).

Appendix 6. Protocol Amendment I6T-MC-AMBD(c) Summary

A Single-Dose Study to Assess the Safety, Tolerability, and Pharmacokinetics of LY3074828 in Healthy Chinese Subjects

Overview

Protocol I6T-MC-AMBD, “A Single-Dose Study to Assess the Safety, Tolerability, and Pharmacokinetics of LY3074828 in Healthy Chinese Subjects”, has been amended. The new protocol is indicated by Amendment (c) and will be used to conduct the study in place of any preceding version of the protocol.

The overall changes and rationale for the changes made to this protocol are as follows:

- The statement that this is a single-site study has been removed throughout in order to allow flexibility in the number of sites at which the study may be conducted.
- A description of how the final report coordinating investigator will be identified if the study is conducted at more than 1 site has been added.

Revised Protocol Sections

Note:	All deletions have been identified by strike-throughs .
	All additions have been identified by the use of underscore .

1. Protocol Synopsis

Summary of Study Design:

Study I6T-MC-AMBD (AMBD) is a ~~single center~~, subject- and investigator-blinded, randomized, parallel-group, placebo-controlled, Phase 1 single-dose study of LY3074828 in healthy Chinese subjects. Native Chinese subjects born in China, with all 4 grandparents and both parents of Chinese origin will be enrolled. The study will consist of 5 planned dose cohorts: 3 intravenous (IV) dose cohorts (300 mg, 600 mg, and 1200 mg) and 2 subcutaneous (SC) dose cohorts (200 mg and 400 mg). Subjects will be randomized within each cohort to receive LY3074828 (10 subjects) or placebo (2 subjects).

5.1 Overall Design

Study I6T-MC-AMBD (AMBD) is a ~~single center~~, subject- and investigator-blinded, randomized, placebo-controlled, parallel-group, Phase 1 single-dose study of LY3074828 in healthy Chinese subjects. Safety, tolerability, and PK of LY3074828 will be evaluated.

12. Appendices

## 2. ABBREVIATIONS

Abbreviations pertain to the Statistical Analysis Plan (SAP) only (not the tables, figures and listings [TFLs]).

|                            |   |
|----------------------------|---|
| AE                         | Adverse event   |
| ADA                        | Anti-drug antibody  |
| ALP                        | Alkaline phosphatase  |
| ALT                        | Alanine aminotransferase  |
| AUC                        | Area under the concentration versus time curve  |
| AUC(0-t last )  | Area under the concentration versus time curve from time zero to time t, where t is the last time point with a measurable concentration |
| AUC(0-∞)                   | Area under the concentration versus time curve from time zero to infinity   |
| %AUC(t last -∞) | Percentage of AUC(0-∞) extrapolated   |
| BMI                        | Body mass index   |
| BQL                        | Below the lower limit of quantification   |
| C last          | Last quantifiable drug concentration  |
| C max           | Maximum observed drug concentration   |
| CI                         | Confidence interval   |
| CL/F                       | Apparent total body clearance of drug calculated after extra-vascular administration  |
| CRF                        | Case Report Form  |
| CRU                        | Clinical Research Unit  |
| CSR                        | Clinical Study Report   |
| CV                         | Coefficient of variation  |
| EC                         | Early Clinical  |
| ECG                        | Electrocardiogram   |
| e.g.                       | For example (Latin: exempli gratia )   |
| F                          | Fraction of extravascular dose reaching the general circulation compared to an IV administration  |
| ICH                        | International Conference on Harmonisation   |
| IV                         | Intravenous   |
| LLOQ                       | Lower limit of quantification   |
| MedDRA                     | Medical Dictionary for Regulatory Activities  |

---

|            |  |
|------------|--|
| MRE        | Magnetic resonance elastography  |
| PK         | Pharmacokinetic  |
| SAP        | Statistical Analysis Plan  |
| SC         | Subcutaneous   |
| SD         | Standard deviation   |
| SOP        | Standard Operating Procedure   |
| $t_{1/2}$  | Half-life associated with the terminal rate constant ( $\lambda_z$ ) in non-compartmental analysis |
| TBL        | Total bilirubin  |
| CCI | [REDACTED]   |
| TEAE       | Treatment-emergent adverse event   |
| TFLs       | Tables, Figures, and Listings  |
| $t_{max}$  | Time of maximum observed drug concentration  |
| ULN        | Upper limit of normal  |
| $V_{ss}$   | Volume of distribution at steady state after intravenous administration                            |
| $V_{ss/F}$ | Apparent volume of distribution at steady state after extra-vascular administration                |
| $V_z$      | Volume of distribution during the terminal phase after IV administration                           |
| $V_z/F$    | Apparent volume of distribution during the terminal phase after extra-vascular administration      |
| WHO        | World Health Organization  |

### **3. INTRODUCTION**

This SAP has been developed after review of the Clinical Study Protocol (final version dated 10 July 2018) and protocol amendment (a) (final version dated 19 September 2018).

This SAP describes the planned analysis of the safety, tolerability and pharmacokinetic (PK) data from this study. A detailed description of the planned TFLs to be presented in the clinical study report (CSR) is provided in the accompanying TFL shell document.

The intent of this document is to provide guidance for the statistical and PK analyses of data. In general, the analyses are based on information from the protocol, unless they have been modified by agreement between Eli Lilly and Company and Covance Early Clinical (EC) Biometrics. A limited amount of information concerning this study (e.g., objectives, study design) is given to help the reader's interpretation. This SAP must be signed off prior to first subject administration for this study. When the SAP and TFL shells are agreed upon and finalized, they will serve as the template for this study's CSR.

This SAP supersedes the statistical considerations identified in the protocol; where considerations are substantially different, they will be so identified. If additional analyses are required to supplement the planned analyses described in this SAP, they may be performed and will be identified in the CSR. Any substantial deviations from this SAP will be agreed upon between Eli Lilly and Company and Covance EC Biometrics and identified in the CSR. Any minor deviations from the TFLs may not be documented in the CSR.

This SAP is written with consideration of the recommendations outlined in the International Conference on Harmonisation (ICH) E9 Guideline entitled Guidance for Industry: Statistical Principles for Clinical Trials and the ICH E3 Guideline entitled Guidance for Industry: Structure and Content of Clinical Study Reports.

### **4. STUDY OBJECTIVE**

#### **4.1 Primary Objective**

- To assess the safety and tolerability of single LY3074828 intravenous (IV) doses (300, 600, and 1200 mg) and single subcutaneous (SC) doses (200 and 400 mg) in healthy Chinese subjects.

#### **4.2 Secondary Objective**

- To evaluate the PK of single LY3074828 IV doses (300, 600, and 1200 mg) and single SC doses (200 and 400 mg) in healthy Chinese subjects.

cc

## 5. STUDY DESIGN

Study I6T-MC-AMBD is a single-center, subject- and investigator-blinded, randomized, parallel-group, placebo-controlled, Phase 1 single-dose study of LY3074828 in healthy Chinese subjects. Safety, tolerability, and PK of LY3074828 will be evaluated.

Native Chinese subjects born in China will be enrolled; all 4 biological grandparents and both biological parents must be of Chinese origin. Every effort should be made to enroll subjects so that at least 4 subjects in each cohort will be female. However, if the desired number of female subjects is not achieved, this will not constitute a protocol deviation.

**Screening Period ( $\leq 28$  days):** Subjects will be evaluated for study eligibility  $\leq 28$  days prior to enrolment.

**Residential Period (3 days/2 nights):** A total of approximately 60 subjects (12 subjects per cohort) who fulfil the eligibility criteria will be enrolled into the study. Subjects will be randomized within each cohort to receive study drug or placebo:

- Cohort 1: a single dose of LY3074828 300 mg or placebo IV infused over at least 30 minutes (10 LY3074828, 2 placebo)
- Cohort 2: a single dose of LY3074828 600 mg or placebo IV infused over at least 60 minutes (10 LY3074828, 2 placebo)
- Cohort 3: a single dose of LY3074828 1200 mg or placebo IV infused over at least 2 hours (10 LY3074828, 2 placebo)
- Cohort 4: a single dose of LY3074828 200 mg or placebo SC (10 LY3074828, 2 placebo)
- Cohort 5: a single dose of LY3074828 400 mg or placebo SC (10 LY3074828, 2 placebo)

Dosing of cohorts may be conducted in parallel or sequentially at the discretion of the investigator. Subjects will report to the clinical research unit (CRU) on Day -1. After randomization, study drug will be administered by investigative site staff by IV administration using a forearm vein or SC injection in the abdomen using pre-filled syringes (PFSs) in the morning of Day 1 after an overnight fast. Subjects will remain at the CRU until the scheduled procedures have been completed on Day 2, and will then be discharged.

**Outpatient Follow-up Period (12 weeks):** The follow-up period will include outpatient visits for a total of approximately 12 weeks (Days 4, 8, 11 [SC only], 15, 22, 29, 43, 57, 71, and 85) following dose administration on Day 1 to assess the safety, tolerability, and PK of LY3074828 in healthy Chinese subjects.

## 6. TREATMENTS

The following is a list of the study treatment abbreviations that will be used in the TFLs. Placebo IV and Placebo SC data may be pooled in the TFLs, as appropriate.

| Study Treatment Name | Treatment order in TFL |
|----------------------|------------------------|
| Placebo IV           | 1                      |
| 300 mg LY3074828 IV  | 2                      |
| 600 mg LY3074828 IV  | 3                      |
| 1200 mg LY3074828 IV | 4                      |
| Placebo SC           | 5                      |
| 200 mg LY3074828 SC  | 6                      |
| 400 mg LY3074828 SC  | 7                      |

## 7. SAMPLE SIZE JUSTIFICATION

Sixty subjects who fulfil the eligibility criteria may be enrolled into the study to try to ensure that approximately 50 subjects (10 subjects per cohort) complete. The number of subjects in Study AMBD is not sufficient for any formal ethnic comparison, but the safety, tolerability, and PK data will be assessed in Chinese subjects and will be used to support the inclusion of Chinese subjects in future studies involving LY3074828.

The sample size is customary for Phase 1 studies evaluating safety and PK, and is not powered on the basis of statistical hypothesis testing.

Subjects who withdraw from the study will not be replaced. For analytical purposes, a subject's study participation is considered as complete if he/she receives the study drug as per the protocol requirements and completes all activities up to and including at least Day 57.

## 8. DEFINITION OF ANALYSIS POPULATIONS

The "Safety" population will consist of all enrolled subjects who received LY3074828 or placebo, and have at least one postdose safety assessment.

The "Pharmacokinetic" population will consist of all subjects who received at least one dose of LY3074828 and have evaluable PK data.

All protocol deviations that occur during the study will be considered for their severity/impact and will be taken into consideration when subjects are assigned to analysis populations.

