10.3. Statistical Analyses

Statistical analysis of this study will be the responsibility of Eli Lilly and Company or its designee.

Pharmacokinetic analyses will be conducted on data from all subjects who receive IP and have evaluable PK. Safety analyses will be conducted for all enrolled subjects, whether or not they completed all protocol requirements. Analysis will be according to the treatment the subjects actually received.

Additional exploratory analyses of the data will be conducted as deemed appropriate. CCI [REDACTED]

No adjustments for multiple comparisons will be made.

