10.3.1.2. Statistical Evaluation of Safety

10.3.1.2.1. Injection-site Pain

The intensity of pain at the injection sites immediately (approximately within 1 minute after start of first injection, designated as “0-hour assessment”) following the start of the first injection will be evaluated, as reported by the subject and measured according to the 0 to 100 mm VAS. Assessments will also be performed at 0.25, 0.5, 1, 2, and 4 hours post first injection; however, the 0-hour assessment will be considered the primary endpoint for injection-site pain assessment.

Descriptive statistics will be used to summarize the intensity of pain at each time point as captured by the VAS.

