Appendix 1. Abbreviations and Definitions

Term	Definition
ADA	anti-drug antibody
AE	adverse event: Any untoward medical occurrence in a patient or clinical investigation subject administered a pharmaceutical product that does not necessarily have a causal relationship with this treatment. An AE can therefore be any unfavorable and unintended sign (including an abnormal laboratory finding), symptom, or disease temporally associated with the use of a medicinal (investigational) product, whether or not related to the medicinal (investigational) product.
ALP	alkaline phosphatase
ALT	alanine aminotransferase
AUC	area under the concentration versus time curve
AUC(0-∞)	area under the concentration versus time curve from time zero to infinity
AUC(0-t_{last})	area under the concentration versus time curve from time zero to time t, where t is the last sample with a measurable concentration
BMI	body mass index
CD	Crohn's disease
CL/F	apparent total body clearance of drug calculated after extra-vascular administration
C_{max}	maximum observed drug concentration
complaint	A complaint is any written, electronic, or oral communication that alleges deficiencies related to the identity, quality, purity, durability, reliability, safety or effectiveness, or performance of a drug or drug delivery system.
compliance	Adherence to all the study-related requirements, good clinical practice (GCP) requirements, and the applicable regulatory requirements.
confirmation	A process used to confirm that laboratory test results meet the quality requirements defined by the laboratory generating the data and that Lilly is confident that results are accurate. Confirmation will either occur immediately after initial testing or will require that samples be held to be retested at some defined time point, depending on the steps required to obtain confirmed results.
CP	clinical pharmacologist
CRP	clinical research physician: Individual responsible for the medical conduct of the study. Responsibilities of the CRP may be performed by a physician, clinical research scientist, global safety physician or other medical officer.
CRU	clinical research unit
ECG	electrocardiogram
eCRF	electronic case report form

enroll	The act of assigning a subject to a treatment. Subjects who are enrolled in the study are those who have been assigned to a treatment.
enter	Subjects entered into a study are those who sign the informed consent form directly or through their legally acceptable representatives.

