## 9. STATISTICAL METHODOLOGY

### 9.1 General

Data listings will be provided for all data that is databased. Summary statistics and statistical analysis will only be presented for data where detailed in this SAP. For continuous data, summary statistics will include the arithmetic mean, arithmetic standard deviation (SD), median, min, max and N; for log-normal data (e.g. the PK parameters: area under the concentration time curve [AUC] and maximum observed drug concentration [ $C_{max}$ ]) the geometric mean and geometric coefficient of variation (CV%) will also be presented. For categorical data, frequency

count and percentages will be presented. Data listings will be provided for all subjects up to the point of withdrawal, with any subjects excluded from the relevant population highlighted. Summary statistics and statistical analyses will generally only be performed for subjects included in the relevant analysis population. For the calculation of summary statistics and statistical analysis, unrounded data will be used.

Mean change from baseline is the mean of all individual subjects' change from baseline values. Each individual change from baseline will be calculated by subtracting the individual subject's baseline value from the value at the time point. The individual subject's change from baseline values will be used to calculate the mean change from baseline using a SAS procedure such as Proc Univariate.

No adjustments for multiple comparisons will be made.

Data analysis will be performed using SAS® Version 9.4 or greater.

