## **9.4 Safety and Tolerability Assessments**

### **9.4.1 Adverse events**

Where changes in severity are recorded in the Case Report Form (CRF), each separate severity of the adverse event (AE) will be reported in the listings, only the most severe will be used in the summary tables. A pre-existing condition is defined as an AE that starts before the subject has provided written informed consent and is ongoing at consent. A non-treatment emergent AE is defined as an AE which starts after informed consent but prior to dosing. A treatment-emergent AE (TEAE) is defined as an AE which occurs postdose or which is present prior to dosing and becomes more severe postdose.

All AEs and product complaints will be listed. TEAEs will be summarized by treatment, severity and relationship to the study drug. The frequency (the number of AEs, the number of subjects experiencing an AE and the percentage of subjects experiencing an AE) of TEAEs will be summarized by treatment, Medical Dictionary for Regulatory Activities (MedDRA) version 21.0 system organ class and preferred term. The summary and frequency AE tables will be presented for all causalities and those considered related to the study drug. Any serious AEs will be listed.

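### Could the deviation sentence in SAP 8 remove a dosed subject from the primary safety summaries?

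*SAP*

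**What the plan says.** SAP 8 has three parts. Safety is every enrolled subject who received LY3074828 or placebo and had some safety assessment after dosing. Pharmacokinetic is every subject who received LY3074828 and has evaluable PK data. A closing sentence says that deviations during the study are weighed for severity and impact and "will be taken into consideration when subjects are assigned to analysis populations". It does not say which population it is aimed at.

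Two rules in SAP 9.1 settle what membership means. For tables: "Summary statistics and statistical analyses will generally only be performed for subjects included in the relevant analysis population". For listings, subjects are shown up to withdrawal, "with any subjects excluded from the relevant population highlighted". SAP 9.4.1 adds: "All AEs and product complaints will be listed".

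Protocol 10.3 gives the parent rule: "Safety analyses will be conducted for all enrolled subjects, whether or not they completed all protocol requirements". It continues: "Analysis will be according to the treatment the subjects actually received". SAP 3 says that the analyses generally rest on the protocol unless modified by agreement. It also says that the SAP takes precedence over the protocol's statistical section and that substantial differences will be identified. SAP 11 reports none.

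The primary endpoints are TEAE incidence and VAS pain score (Protocol 4). For pain, "the 0-hour assessment will be considered the primary endpoint for injection-site pain assessment" (Protocol 10.3.1.2.1).

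**The concern.** A safety population normally includes everyone who was treated, and deviations normally matter only for PK or per-protocol sets. Here the deviation sentence follows both definitions, refers to populations in the plural and leaves Safety unprotected. It gives no deviation types, threshold, decision-maker or timing. Because it concerns deviations arising during the study, each judgement comes after the SAP has been signed.

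Other parts of the plan sharpen the worry. The sponsor is unblinded (Protocol 7.3), and data may be accessed and analysed while the trial runs (Protocol 10.3.6). The protocol also foresees dosed subjects with deviations: an inadvertently enrolled subject may continue (8.1.1), and overdose is addressed (9.3).

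If such a subject were dropped after the data had been seen, a primary descriptive result could move either way, in groups of 4 to 10. The listings would reveal the exclusion, but the tables would stand. That would sit badly with Protocol 10.3 and with the SAP's statement that nothing had changed.

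**Working it through.** **Group sizes.** Five cohorts of 12 give 5 × 12 = 60, the planned enrolment. Each cohort has 10 active and 2 placebo subjects (SAP 5). With the treatment labels in SAP 6:

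- each active group: n = 10
- Placebo IV: 3 × 2 = 6
- Placebo SC: 2 × 2 = 4
- placebo pooled across routes, which SAP 6 allows: 6 + 4 = 10

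**What one exclusion would do to TEAE incidence.** With k affected subjects among n, incidence is k/n. Dropping an affected subject gives (k − 1)/(n − 1). Dropping an unaffected one gives k/(n − 1). The case k = 1 is an assumption, for illustration only.

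| Group | All kept | Affected subject dropped | Unaffected subject dropped |
|---|---|---|---|
| Active, or pooled placebo, n = 10 | 1/10 = 10.0% | 0/9 = 0% | 1/9 = 11.1% |
| Placebo IV, n = 6 | 1/6 = 16.7% | 0/5 = 0% | 1/5 = 20.0% |
| Placebo SC, n = 4 | 1/4 = 25.0% | 0/3 = 0% | 1/3 = 33.3% |

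**What it would do to the VAS mean (Cohorts 4 and 5 only).** Dropping a subject whose score is d above the group mean m gives (n·m − m − d)/(n − 1) = m − d/(n − 1). For an assumed d = 30 mm, the shift is 30/9 = 3.3 mm at n = 10 and 30/3 = 10 mm at n = 4. Pooling across routes does not help here, because IV subjects have no VAS score.

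**Loss of information alone.** With no events, the one-sided 95% upper bound on incidence is 1 − 0.05^(1/n): 25.9% at n = 10 and 28.3% at n = 9. Losing one subject costs little precision. Any harm would come from choosing whom to lose.

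**Does the plan lead to such an exclusion?**

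1. The Safety definition is specific and inclusive, with two conditions: dosed, and assessed afterwards. A deviation is not among its grounds for exclusion. The closing sentence is general, asks only that deviations be considered, and does not say that a subject meeting the definition is removed.
2. The sentence has natural work to do in the Pharmacokinetic definition. Whether PK data are evaluable calls for judgement, and a dosing or sampling deviation bears on it directly.
3. Protocol 10.3 keeps subjects in the safety analyses even if they did not complete all requirements. SAP 3 starts from the protocol and SAP 11 declares no departure. Read together, the documents keep dosed subjects in Safety and carry over the as-treated rule, which the SAP omits but does not contradict.
4. The condition of a postdose assessment will rarely matter. Subjects stay in the unit until Day 2, with AE review and 6-hour vital signs on Day 1, and SC subjects are assessed within minutes of the first injection.
5. The protocol's enrolled set is wider on paper: "Subjects who are enrolled in the study are those who have been assigned to a treatment". A randomized but undosed subject cannot have a TEAE, which SAP 9.4.1 defines relative to dosing, nor a 0-hour VAS score. Such a subject could only inflate a denominator.

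Applied as written, the Safety denominators are 10, 6 and 4 if all are dosed, and the single assumed event stays visible as 1/10.

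**The case for a change.** The strongest opposing case is that the text should not rely on goodwill. The SAP claims precedence over the protocol, so Protocol 10.3 cannot simply be assumed to override SAP 8. The deviation sentence is not limited to PK. PK values have a written outlier procedure that bars dropping complete profiles, whereas decisions on Safety membership have nothing comparable. With an unblinded sponsor and no stated time for fixing the populations, a discretionary exclusion is possible. With no inferential analysis planned, the descriptive tables are the primary result. A clarifying sentence would cost almost nothing.

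Much of this is accurate. The sentence is loosely drafted, severity and impact are not operational criteria, and the arithmetic above is right. What does not follow is that the tables are at real risk. The sentence permits exclusion at most and never requires it, and using it against Safety means letting a general remark defeat a specific definition. The opportunity is also narrow: one dose, given at the site (Protocol 7.6), with no dose adjustments (7.4). An exclusion would be plain in the listings, and the affected subject's AEs would be there too. The most striking TEAE figures depend on presenting SC placebo separately at n = 4. Finally, a clarification would record what analysts following the definition already do, so no result would change.

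**Conclusion.** No change to the plan follows. SAP 8 leaves a small gap: it does not say that deviations leave Safety membership untouched. Its own Safety definition, read with Protocol 10.3, fills that gap in the usual way, and every dosed and assessed subject enters the TEAE summary and, for SC cohorts, the VAS summary. If the sentence were misused, one exclusion could move TEAE incidence from 10% to 0% in an active group, or from 25% to 0% in an unpooled SC placebo group. It could move a VAS mean by 3.3 to 10 mm. These figures rest on one assumed event and an assumed 30 mm distance from the mean, and nothing in the documents makes such an exclusion likely. No test, power or error rate is involved.

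The conclusion assumes that the general sentence does not override the specific definition. One point cannot be fully checked. The SAP was written against the original protocol and amendment (a), while the protocol available is amendment (c). The amendment (c) summary describes only changes about the number of sites and the coordinating investigator, but the intervening text is not available. Whether SAP 11 was exact when signed therefore stays open, without affecting who is counted in the safety tables.
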